# For the elderly subjects (age ≥65 years old and ≤85 years old)

#### **Inclusion criteria:**

- 1. Male or female subjects ≥65 years old and ≤85 years old at Screening Visit.
- Individuals who are in a health condition that can receive the investigational vaccine, at the time of entry into
  the trial as determined by medical history, physical examination (including vital signs, ECG) and eligibility
  screening tests (hematology, biochemistry and urinalysis) and clinical judgment of the investigator at
  Screening Visit.
- 3. The subject can provide with informed consent and signs and dates a written informed consent form (ICF) prior to the initiation of any trial procedures.
- 4. They must be able to understand and follow trial-related instructions.
- 5. They must be willing and able to comply with planned visits, treatment schedule, laboratory tests and other requirements of the trial.
- 6. Negative in antibodies screening of SARS-CoV-2 (blood samples from fingertip).
- 7. No imaging features of COVID-19 in chest CT.
- 8. Axillary temperature≤37.0° C.
- 9. Negative SARS-CoV-2 test in throat swabs by RT-PCR.
- 10. Women of childbearing potential (WOCBP) must have a negative serum β-hCG at Screening Visit. Women that are postmenopausal (Menopause ≥ 12 consecutive months) or permanently sterilized will be considered as not having reproductive potential.
- 11. WOCBP must have used effective contraception 14 days prior to screening and agree to use effective contraception continuously during the trial period, from 14 days prior to Screening Visit to 60 days after the last immunization.
- 12. WOCBP must agree not to donate eggs (ova, oocytes) for the purposes of assisted reproduction during trial, starting from Screening Visit and continuously until 60 days after be given the last immunization.
- 13. Men who are sexually active with a WOCBP and have not had a vasectomy must agree to practice a effective form of contraception with their female partner of childbearing potential during the trial, starting from Screening Visit and continuously until 60 days after be given the last immunization.
- 14. Men must be willing to refrain from sperm donation, starting from Screening Visit and continuously until 60 days after receiving the last immunization.

#### **Exclusion criteria:**

- 1. Baseline laboratory abnormalities with Grade ≥3 (for hematology abnormalities with Grade ≥2, according to the grading criteria in appendix B) during screening visits, by physical examination and eligibility screening.
- 2. Have had any acute illness, as determined by the investigator, with or without fever, within 72 h prior to the prime vaccination. An acute illness which is nearly resolved with only minor residual symptoms remaining is allowable if, in the opinion of the investigator, the residual symptoms will not compromise their well-being if they participate as trial subjects in the trial, or that will not prevent, limit, or confound the protocol-specified assessments.
- 3. Have a known allergy, hypersensitivity, or intolerance to the planned vaccine for trial including any excipients.

- 4. Used to have a history of hypersensitivity or serious reactions to vaccination.
- 5. Received any vaccination within 4 weeks prior to Visit 1.
- 6. Don't agree to not be vaccinated during the trial, starting from Screening Visit and continuously until 28 days after receiving the last immunization, except emergency vaccination (e.g. rabies vaccine, tetanus vaccine).
- 7. Had administration of any immunoglobulins and/or any blood products within the 3 months prior to Screening Visit.
- 8. Had any serious or life-threatening medical condition (e.g., autoimmune disease, cardiovascular disease) within the past 5 years, which in the opinion of the investigator, could compromise their well-being if they participate as trial subjects in the trial, or that could prevent, limit, or confound the protocol-specified assessments.
- 9. Have any surgery planned during the trial, starting from Screening Visit and continuously until at least 90 days after the last immunization.
- 10. Had any chronic use (more than 14 continuous days) of any systemic medications that affects immune function, including immunosuppressant or other immune-modifying drugs, within 6 months prior to Screening Visit unless in the opinion of the investigator, the medication would not prevent, limit, or confound the protocol-specified assessments or could compromise safety of subjects.
- 11. Had administration of another investigational product including vaccines within 60 days or 5 half-lives (whichever is longer), prior to Screening Visit.
- 12. With known history of AIDS or HIV test positive.
- 13. History of HBV or HCV infection.
- 14. History of SARS, SARS-CoV-2 or MERS infection. Suspected SARS patients should be screened for SARS antibodies.
- 15. Previously participated in a clinical trial involving lipid nanoparticles.
- 16. Are subject to exclusion periods of other clinical trials or simultaneous participation in another clinical trial.
- 17. Have any affiliation with the study site (e.g., are close relative of the investigator or dependent person, such as an employee or student of the study site).
- 18. Have a history of drug abuse or known medical, psychological, or social conditions within the past 5 years. In the opinion of the investigator, could comprise their well-being if they participate as trial subjects in the trial, or that could prevent, limit, or confound the protocol-specified assessments.
- 19. Have a history of narcolepsy.
- 20. Have history of alcohol abuse or drug addiction within 1 year prior to Screening Visit.
- 21. Have a history of or suspected immunosuppressive condition, acquired or congenital, as determined by medical history and/or physical examination at Screening Visit.
- 22. Have any abnormality or permanent body art (e.g., tattoo), in the opinion of the investigator, would obstruct the ability to observe local reactions at the vaccination site.
- 23. Have had any blood loss >400 mL, e.g., due to donation of blood or blood products or injury, within the 28 days prior to Screening Visit or plan to donate blood or plasma during the trial, starting from Screening Visit and continuously until at least 28 days after be given the last immunization.
- 24. Travel or live in any country or region with a high SARS-CoV-2 infection risk (as defined at Screening Visit) within the 14 days prior to Screening Visit.
- 25. They plan to visit any country or region with a high SARS-CoV-2 infection risk (as defined at Screening

Visit), from Screening Visit until 14 days after be given the last immunization.

- 26. Symptoms of COVID-19, e.g., respiratory symptoms, fever, cough, shortness of breath and breathing difficulties.
- 27. Have had contact with confirmed COVID-19 patients or persons tested positive for SARS-CoV-2 within the 30 days prior to Screening Visit.
- 28. Are vulnerable persons, e.g., soldiers, subjects in detention, CRO or Fosun staffs or their family members.

#### **Trial Vaccines:**

# Investigational Vaccine:

The drug product is a preservative-free, sterile dispersion of RNA formulated in lipid nanoparticles (LNP) in aqueous cryoprotectant buffer for intramuscular administration. The RNA drug substance is the only active ingredient in the drug product. The composition meets the supplier's specifications. For dispensing and operation protocol, see Pharmacy Manual.

Frequency of Two injections (21 days apart).

vaccination:

Route of Intramuscular (IM); upper arm, musculus deltoideus; the P/B regimens. The same vaccination: arm may be used for both immunizations. The non-dominant arm is preferred.

#### Placebo:

NaCl 0.9% solution is being used as placebo. It is a sterile, clear, colorless liquid solution of sodium chloride without preservative designed for parenteral use only. Placebos are commercially packaged and stored according to the labeling. The placebo is vaccinated by IM at 21-day intervals.

#### **Duration of the trial/Evaluation period:**

Approximately 12 months (after screening period).

#### **Primary endpoints**

*Safety and tolerability of BNT162b1, as determined by:* 

- Occurrence of solicited local reactions in the subjects (eg, vaccination sites: pain/tenderness, erythema/redness, induration/swelling) during the 14-day after each dose of BNT162b1 or placebo.
- Occurrence of solicited systematic reactions (eg, nausea, vomiting, diarrhea, headache, fatigue, myalgia, arthralgia, chills, loss of appetite, malaise and fever) during 14-day after each dose of BNT162b1 or placebo.
- Occurrence of AE associated with vaccination in subjects during the 21-day period after prime vaccination and the 28-day period after boost dose of BNT162b1 or placebo.

#### **Secondary endpoints**

Safety and tolerability of BNT162b1, as determined by:

[figure not shown]
- The proportion of subjects experiencing SAEs, occurring up to Day 21 after prime vaccination and Day 28 after boost vaccination, up to Month 3, 6 and 12.
- The proportion of subjects experiencing AE associated with BNT162b1, occurring up to Month 3, 6 and 12.
- The proportion of of subjects experiencing abnormal markers of hematology, blood chemistry and urine analysis, occurring at Hour 24 and Day 7 after prime vaccination and at Day 7 after boost dose of BNT162b1 or placebo.

*Immunogenicity of BNT162b1, as determined by:* 

• Geometric mean titer (GMT) of anti-S1 IgG antibody at Day 7, Day 21 after prime vaccination, at Day 7, Day 21 after boost vaccination, and at Month 3, 6 and 12.

- Geometric mean titer (GMT) of anti-RBD IgG antibody at Day 7, Day 21 after prime vaccination, at Day 7, Day 21 after boost vaccination, and at Month 3, 6 and 12.
- GMT of SARS-CoV-2 neutralizing antibody (including true virus-based SARS-CoV-2 neutralizing antibody assay) at Day 7, Day 21 after prime vaccination, at Day 7, Day 21 after boost vaccination, and at Month 3, 6 and 12.
- Fold increase in antibody anti-S1 IgG antibody titers, as compared to baseline, at Day 7, Day 21 after prime vaccination, at Day 7, Day 21 after boost vaccination, and at Month 3, 6 and 12.
- Fold increase in antibody anti-RBD IgG antibody titers, as compared to baseline, at Day 7, Day 21 after prime vaccination, at Day 7, Day 21 after boost vaccination, and at Month 3, 6 and 12.
- Fold increase in SARS-CoV-2 neutralizing antibody titers (virus neutralizing test), as compared to baseline, at Day 7, Day 21 after prime vaccination, at Day 7, Day 21 after boost vaccination, and at Month 3, 6 and 12.
- Seroconversion rates (SCR), defined as a minimum of 4-fold increase of antibody titers, as compared to baseline, at Day 7, Day 21 after prime vaccination, and at Day 7, Day 21 after boost vaccination.

#### **Exploratory endpoints**

#### **Statistical Considerations:**

#### Analysis sets:

- Safety Set: Safety Set will consist of all randomized subjects who receive at least one dose of the investigational vaccine/placebo and at least one safety evaluation.
- Total Vaccinated Cohort (TVC): According to intention-to-treat analysis set principle, the TCV will include all randomized subjects who have received at least one dose of the investigational vaccine/placebo and provided valid baseline.
- Per protocol set (PPS): The PPS will include all subjects in the TVC who have no major protocol violations and complete boost vaccination. The protocol violation criteria will be defined as part of the blinded data review. The categories of major protocol violations include:
  - 1 not meeting inclusion criteria, or meeting exclusion criteria,
  - 2 receiving a wrong investigational vaccine/placebo,
  - 3 receiving prohibited therapies,
  - 4 other major protocol violations that be identified during blinded data reviews.

All summaries and analyses of safety data will be based on subjects in the Safety Set.

The primary immunogenicity endpoint analyses will be based on the PPS and TVC, and additional immunogenicity endpoint analyses will be based on the TVC.

Demographics and other baseline characteristic analysis: Summaries of age, gender, race, and other baseline characteristics will be presented by groups of BNT162b1 and placebo.

Immunogenicity analysis: Descriptive statistics for the primary and secondary immunogenicity endpoints, including estimates and 95% confidence intervals (95% CI) for GMT and SCR, will be provided by time point and by different age's groups, different dose cohorts of BNT162b1 and placebo group. Different BNT162b1 dose cohorts will be compared in pairs, and the GMT ratio of each two dose cohorts as well as the point estimate value of SCR difference and 95% CI will be calculated. Generally, immunogenicity will be summarized and analyzed based on age groups and dose cohorts.

- Seronegative subjects: subjects with no detectable serum antibodies (test results are below Lower Limit of Detection) as measured by ELISA/neutralization assay.
- Seroconverted subjects: By ELISA/neutralization detection, the subject whose serum antibodies titers after
  vaccination of subjects are at least 4 times higher than baseline. If the baseline did not reach the lower limit
  of titer detection, the positive conversion is defined as the antibody titer reaching at least 4 times of the lower
  limit.

Safety analysis: Within 14 days after each vaccination (Including the day of vaccination of vaccine/placebo), by collecting soliciting AE, including local reactions (Vaccination site: pain/tenderness, erythema/redness, induration/swelling) and general reactions (nausea, vomiting, diarrhea, headache, fatigue/tiredness, myalgia, arthralgia, chills loss of appetite, malaise and fever), to evaluate reactogenicity. In addition, body temperature (axillary) as indicator of reactogenicity will be collected (with fever defined as axillary temperature  $\geq 37.3^{\circ}$ C, oral temperature  $\geq 38.0^{\circ}$ C).

For each solicited reaction, including fever, the percentage of subjects will be summarized by event severity for each day within 14 days after each vaccine/placebo vaccination and overall.

All AEs and SAEs will be coded using the Medical Dictionary for Regulatory Activities (MedDRA version 23.0) and summarized by system organ class (SOC) and preferred term (PT) for each group (BNT162b1 and placebo) including aggravation after vaccination and new medical conditions.

Safety summaries will be provided by different age groups and different dose cohorts/placebo groups.

#### **Sample Size Justification:**

This study is a phase 1 exploratory clinical trial.

In the study, approximately 24 subjects will be included in each dose cohort of each age group, another 24 subjects vaccinated with placebo. If the occurrence of TEAE is 8%, the probability of observation of at least one TEAE in 24 subjects in each dose group is 86.5%, which is sufficient to perform safety evaluation for investigational vaccine at each dose level.

#### **Timepoint of Statistical Analysis:**

#### Initial analysis:

In the study, all available safety and immunogenicity data will be included when all subjects in each age group complete Visit 9 (Day 50, 28 days after boost vaccination) to perform initial analysis. When all subjects in each age group complete Visit 11 (visit at Month 6 after prime vaccination), Viisit 12 (visit at Month 12 after prime vaccination), and an overall analysis will be performed.

Unblinding will be occurred at the initial analysis of safety and immunogenicity 28 days after boost inoculation, but the subjects will be kept blinded. More details regarding the analyses will be provided in the Statistical Analysis Plan (SAP).

The analysis report will be prepared after each phase of analysis and the overall study report will be prepared at the end of study.

#### **Safety Review Committee (SRC):**

Safety Review Committee (SRC) will be established comprising investigators, Fosun medical representatives, and medical monitor, etc.

Key roles of the SRC are as follows:

- Before progression to the next age group (elderly group), assess the safety and tolerability data of the subjects completed safety visits up to 14 days after prime vaccination, and decide whether to approve initiation of the dose cohort of elderly group. Data collected include vital signs, TEAEs, local reactions, blood/clinical laboratory data, and brief physical examination outcome.
- Before each dose cohort begins boost vaccination, for each dose cohort, assess the safety and tolerability data of the prime vaccination of subjects (including data collected at least up to 14 days post-vaccination) and, decide whether to approve initiation of boost vaccination of this dose cohort. Data collected include vital signs, TEAEs, local reactions, blood/clinical laboratory data, and brief physical examination outcome.
- Throughout the trial, assess whether to replace trial subjects permanently discontinued due to safety issues.
- Throughout the trial, the SRC may specific additional dose levels to be tested and an appropriate regime for enrollment and safety oversight.

See SRC charter for more information. The SRC will act according to written procedures described in SRC charter.

#### **Independent Data Monitoring Committee:**

The study will be overseen by an Independent Data Monitoring Committee (IDMC). IDMC will consist of 3 or 5 independent members (including epidemiologist, clinical experts, and statistical expert) and 1 independent non-voting statistician.

The IDMC is required to review the unblinded data when a significant event or risk that could cause the study to be suspended occurs. Based on the results of the safety data review, IDMC can request the suspension of investigation in a certain dose group/age group, or suspension of boost vaccination, and can also provide recommendations for subsequent development based on the periodical study data. This study will proceed in accordance with the protocol-specified procedures if no IDMC recommendation for suspension or modification is received.

The IDMC meetings will consist of open and closed face-to-face meetings or teleconference calls. The type and frequency of scheduled meetings will depend on the subject enrollment and safety event rates. Unscheduled ad hoc meetings will occur if a stopping rule occurs, or at any time consultation is requested by the Pharmacovigilance Study Team.

The IDMC will review safety data on an ongoing basis, when the reported AEs meet with the dose-limiting toxicity (DLT) criteria, the IDMC will review all relevant safety data and consider a possible pause of the study, if it deems necessary:

See IDMC charter for more information. The IDMC will act according to written procedures described in IDMC charter.

BNT162-03 Version 3.0 (5 AUG 2020)

Table 2 Schedule of activities

# 1-1 Schedule of activities of adult subjects

Procedure/Assessment	Visit 0	Visit 1 Before prime vaccination	Visit 1 Prime vaccination & after vaccination		Visit 3 7 days after prime vaccination	Visit 4 14 days after prime vaccination	Visit 5 Before boost vaccination		Visit 6 7 days after boost vaccination		Visit 8 21 days after boost vaccination	Visit 9 28 days after boost	Visit 10	Visit 11	Visit 12
Time Points	Screening D -14~D 0		Day 1	24 h (±2 h)	Day 8 (±1 d)	Day 15 (±1 d)	Day 22 (±2 d)	Day 22 (±2 d)	Day 29 (±3 d)	Day 36 (±3 d)	Day 43 (±4 d)	Day 50 (±4 d)	Month 3 (D 85 ±7d)	Month 6 (D 184 ±9d)	Month 12 (D 366 ±9d)
Informed consent	x														
Inclusion/exclusion criteria	x	x (review)			no.										
Demographic data a	x	- 10													
Medical history (incl. alcohol intake) b	x	x (update)													
Travel history and contact history	x	x		x	x	x	x		x	х	x	x	x	x	x
Physical Examination c	x	x	х		x	x	x		x	x	x	x	x	x	x
Vital signs d	x	x	х	x	x	x	x	x	x	x	x	x	x	x	x
12-lead ECG	x	2,		3											8
Chest CT scan	x														
WOCBP serum pregnancy test e	х						х								
Clinical laboratory tests (urine routine) f	x			x	х				х						
Clinical laboratory tests (blood routine, blood chemistry) g	x			x	x				х						
Clinical laboratory tests (thyroid function) h	x			® X					x					x	
Clinical laboratory tests (coagulation function) i	x	35		x	.35				x	)3 					
HIV test (fingertip blood)	x			N				5							

Procedure/Assessment	Visit 0	Visit 1 Before prime vaccination	Visit 1 Prime vaccination & after vaccination		Visit 3 7 days after prime vaccination	Visit 4 14 days after prime vaccination	Visit 5 Before boost vaccination		The second secon	Visit 7 14 days after boost vaccination		Visit 9 28 days after boost		Visit 11	Visit 12
Time Points	Screening D -14~D 0	200000000000000000000000000000000000000	Day 1	24 h (±2 h)	Day 8 (±1 d)	Day 15 (±1 d)	Day 22 (±2 d)	Day 22 (±2 d)	Day 29 (±3 d)	Day 36 (±3 d)	Day 43 (±4 d)	Day 50 (±4 d)	Month 3 (D 85 ±7d)	Month 6 (D 184 ±9d)	Month 12 (D 366 ±9d)
SARS-CoV-2 testing j	x														
Treatment Randomization k		x	3					5	3						
Immunization 		J.S	x	80				х		9					
Collect blood samples for IgG antibody		х			Ä		x		х	× 1	x		x	х	x
Collect blood samples for neutralizing antibody		x					х		x		x		x	х	х
Collect blood samples for CMI test m		х							х		х			×	
Issue subject diaries n		2,	х		x	х		x	х	х	x				
Collect subject diaries		38 8		x	x	х	x	2	х	x	х	x			
Record AEs since last visit	x	x	x	x	x	x	x	x	x	x	x	x	x	x	x
Local reaction assessment o			х	x	x	x	x	x	x	x	x	х			
Record concomitant medications/ products/ vaccinations		x	x	x	x	x	x	x	x	x	x	x	₹ X	x	x
Ask about the health condition of subject	x	x	x	x	x	x	x	x	х	x	х	x	x	x	x

a Demographic information, to be obtained at Screening Visit, will include age (date of birth), sex, race, and ethnicity as provided by the subject.

Medical history (incl. alcohol intake) will be collected at Screening Visit and at Visit 1 (Day 1) and will include any medical history that may be relevant to subject eligibility for trial participation such as prior vaccinations, concomitant medications, and previous and ongoing illnesses or injuries. Relevant medical history can also include any medical history that contributes to the understanding of an AE that occurs during trial participation, if it represents an exacerbation of an underlying disease/preexisting problem. Adverse occurrences before the prime vaccination of investigational vaccine/placebo are considered medical history.

<sup>c Complete physical examination (including height and weight) will be performed at Screening Visit. All subsequent are brief (symptom-directed) physical examinations, performed if deemed necessary or indicated by review of the subject's medical history, should assess clinically significant changes from the baseline examination. The findings

- should be documented in the subject's source document and transcribed into the electronic Case Report Form (eCRF). For any procedures at the site, the investigator shall follow his/her standard practice.
- d Vital signs will be performed at each on site visit, and at 1, 3, and 6 h (±15 min) post each immunization. Vital signs include systolic/diastolic blood pressure, pulse rate, respiratory rate, and body temperature.
- e In WOCBP women only: collect blood sample for testing β-hCG.
- f Urine analysis: glucose, bilirubin, ketone, specific gravity, blood, pH, protein, urobilinogen, nitrite, and leukocytes. Microscopic urinalysis (based on dipstick results): urine sediment will be microscopically examined for the presence of red blood cells, white blood cells, casts, crystals, epithelial cells, and bacteria.
- g Clinical laboratory: (Chemistry) alkaline phosphatase, creatinine, ferritin, C-reactive protein, albumin, alanine aminotransferase, amylase, aspartate aminotransferase, gamma glutamyl transpeptidase, total bilirubin, blood urea, fasting blood sugar, lipase, sodium, potassium, calcium; (Hematology) hemoglobin, hematocrit, red blood cell count, white blood cell count and differential (neutrophils, lymphocytes, monocytes, eosinophils, basophils), platelet count.
- h Clinical laboratory tests (thyroid function): triiodothyronine (T3), thyroxine (T4), thyroid stimulating hormone.
- i Clinical laboratory tests (coagulation function): prothrombin time (PT), activated partial thromboplastin time (APTT), thrombin time (TT)), fibrinogen (FIB).
- j SARS-CoV-2 testing, including RT-PCR test of nasopharyngeal swabs and SARS-CoV-2 antibodies screening. See Appendix C for procedures of collecting and handling specimens of nasopharyngeal swabs.
- k Eligible virus naïve subjects with normal chest CT image enrolled at Screening will enter each cohortwill be randomized to vaccination of BNT162b1 or placebo at Visit 1, within 7 days after Screening Visit 0.
- Each randomized subject will receive two doses of either BNT162b1 (10 or 30 μg) or placebo intramuscularly (IM) one vaccination each at Visit 1 (on Day 1) and at Visit 5 (on Day 22), conduct injections at one third of the deltoid muscle (preferably in the non-dominant arm).
- n Each subject will receive diary cards to collect solicited reactions for 14 days after each vaccination (including the days of vaccine/placebo vaccination), and unsolicited AEs for 21 days after prime vaccination and 28 days after boost (including the days of vaccine/placebo vaccination).
- o From the beginning of prime vaccination to 28 days after boost, local reaction assessment should be conducted at 1, 3 and 6 h (±15 min) after each vaccination and at each site visit after vaccination.

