#### Vaccination protocol and visit schedule

Each randomized subject will be given two doses of either BNT162b1 (10 or 30 μg) or placebo intramuscularly (IM) – one vaccination at Visit 1 (on Day 1) and one vaccination at Visit 5 (on Day 22), into one third of the deltoid muscle, preferably in the non-dominant arm.

From the treatment randomization, each subject will be required to attend 12 clinical visits:

All immunized subjects will attend Visit 1 (prime vaccination) on Day 1, Visit 2 on Day 2 (24 hours after prime vaccination), Visit 3 on Day 8 (7 days after prime vaccination), Visit 4 on Day 15 (14 days after prime vaccination), Visit 5 on Day 22 (boost vaccination), Visit 6 on Day 29 (7 days after boost vaccination), Visit 7 on Day 36 (14 days after boost vaccination), Visit 8 on Day 43 (21 days after boost vaccination), Visit 9 on Day 50 (28 days after boost vaccination), Visit 10 at Month 3, Visit 11 at Month 6 and Visit 12 at Month 12.

Blood samples of subjects in adult group will be collected at the following visits for different tests: at Screening Visit (Visit 0) for eligibility screening tests (including clinical laboratory), at Visits 2, 3, 6 for routine safety laboratory testing (visits 2, 6 coagulation function test, visit 2, 6, 11 thyroid function test), at Visit 1 (prior to prime vaccination) and Visits 5 (prior to boost vaccination), 6, 8, 10, 11, 12 for humoral immunity (antibody). Blood sample will be collected at Visit 1 (prior to prime vaccination) and Visits 6, 8, 11 for cell-mediated immunity (CMI). Urine samples will be collected at Screening Visit (Visit 0) for eligibility screening and collected at Visits 2, 3, 6 for regular safety laboratory testing; serum samples of women of childbearing potential will be collected at Screening Visits (Visit 0) and Visit 5 (prior to boost vaccination) for pregnancy test. Fingertip blood will be collected during the screening visit (visit 0) for detection of SARS-CoV-2 antibody and HIV antibody.

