# **5.1.3** Exploratory objective

## 5.2 Endpoints

# 5.2.1 Primary endpoints

*Safety and tolerability of BNT162b1, as determined by:* 

- Occurrence of solicited local reactions in the subjects (eg, vaccination sites: pain/tenderness, erythema/redness, induration/swelling) during the 14-day after each dose of BNT162b1 or placebo.
- Occurrence of solicited systematic reactions (eg, nausea, vomiting, diarrhea, headache, fatigue, myalgia, arthralgia, chills, loss of appetite, malaise, and fever) during 14-day after each dose of BNT162b1 or placebo.

• Occurrence of AE associated with vaccination in subjects during the 21-day period after prime vaccination and the 28-day period after boost dose of BNT162b1 or placebo.

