- O The collection on the diary card of body temperature, solicited local reactions, and solicited systemic reactions will continue for a total of 14 days following each vaccine/placebo administration. The collection on the diary card of unsolicited AEs and medications will continue for 21 days following prime vaccination and 28 days following boost vaccination.
- The healthcare professional reviewing the data on the diary cards will discuss the AEs (if any) reported by the subject and will determine if any additional diagnoses and/or AEs are present and/or concomitant medications have been used.
- 3. At Visit 5 (Day 22), review the previous diary card with the subject and collect it.
- 4. Provide contraception guidance (see Section 9.1.8).
- 5. Provide the subject with a written reminder of the next planned trial activity. The subject will be reminded to complete the diary card daily and to contact the study site if there are any questions and to contact the site immediately (or as soon as the subject is medically stable) if the subject has a medical condition that leads to a hospitalization or an emergency room visit or is otherwise perceived as serious. Available contact details will be provided to the subjects.
- 6. Schedule the next site visit with the subjects.

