#### 10.2.2 Collection and reporting of unsolicited AEs

Unsolicited AE occurring within 21 days after the prime vaccination and within 28 days after boost vaccination of vaccine/placebo will be collected on diary card (ie, day 22 to day 50 of the trial). AEs leading to withdrawal or discontinuation will be collected throughout the trial. Investigators should report collections of signs and symptoms as diagnosis AEs e.g. 'flu-like symptoms' or 'injection site reaction'.

Related AE/SAE occurring after 28 days after boost vaccination should also be collected and reported.

The following information will be documented for each event:

- Reported term for the Adverse Event,
- Start and end date,
- Serious (Y/N),
- Severity should be judged clinically by the investigator according to the grading standard in 10.3.1. For reference to the specific events listed in Appendix B and Appendix C, refer to the grading standards of the corresponding guidelines.
- Investigator's opinion on the causality (relationship) between the event and administration of trial vaccine(s),

- Investigator's opinion of the causality (relationship) to trial procedure(s), including the details of the suspected procedure,
- Actions taken,
- Outcome of event.

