7.1.3 The Window of Analysis

For visits after baseline, all analyses will be conduct based on the scheduled visit in the protocol, and the unscheduled visits will not be included in the summary tables but be included in the listings.

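### Post-boost visit windows are set on trial day while endpoints run from the boost, so the 7-day sample can be mistimed and the 28-day diary can close early

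*Protocol*

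**What the plan says.** **Visit windows.** Protocol Table 2, schedule 1-1 (adults), gives the boost visit (before and after injection) and Visits 6 to 9 as "Day 22 (±2 d) Day 22 (±2 d) Day 29 (±3 d) Day 36 (±3 d) Day 43 (±4 d) Day 50 (±4 d". Schedule 2-1 (elderly) has the same windows. The synopsis also names each visit by its distance from the boost, for example "Visit 6 on Day 29 (7 days after boost vaccination".

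**Endpoints.** These run from the boost. Protocol 5.2.1 takes vaccination-associated AEs over "the 28-day period after boost dose of BNT162b1 or placebo". Protocol 5.2.2 and SAP 5.1 place antibody endpoints at Days 7 and 21 after boost, and Protocol 5.2.2 places laboratory abnormalities at Day 7 after boost.

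**Diary.** Protocol 9.3.4 says collection of "unsolicited AEs and medications will continue for 21 days following prime vaccination and 28 days following boost vaccination". Footnote n to Table 2 adds the counting rule: "28 days after boost (including the days of vaccine/placebo vaccination". The row "Collect subject diaries" is last marked at Visit 9, and the issue row is last marked at Visit 8. Section 10.2.2 translates the post-boost period into trial days: "within 28 days after boost vaccination of vaccine/placebo will be collected on diary card (ie, day 22 to day 50 of the trial".

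**Delayed boost.** Protocol 6.7 allows the boost after its visit window has passed and does not say whether later visits move with it.

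**Analysis.** SAP 7.1.3 states that for post-baseline visits "all analyses will be conduct based on the scheduled visit in the protocol". It sets no window on actual days since boost.

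**The concern.** The boost and the visits after it each have their own tolerance, both measured from Day 1. The two tolerances therefore add when the interval from boost to visit is calculated. A site that follows Table 2 exactly can draw the 7-day sample well before or well after seven days. It can also collect the last diary before the period that the primary AE endpoint covers has ended.

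Two things are at stake. First, unsolicited AE follow-up may be incomplete by diary, and unequal between subjects, within the 28-day primary window. Second, the antibody and safety laboratory results reported as Day 7 after boost may mix quite different intervals. Protocol 4.2.4 reports the foreign antibody data at seven days after the second dose, and Protocol 4.2.6 says the trial is meant to confirm comparability with foreign subjects. That comparison is not randomized, so balance between arms does not protect it from a timing shift.

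**Working it through.** **Inputs (Protocol Table 2, both schedules).** Boost Day 22 ±2, so Days 20 to 24. Visit 6 Day 29 ±3 (26 to 32). Visit 7 Day 36 ±3 (33 to 39). Visit 8 Day 43 ±4 (39 to 47). Visit 9 Day 50 ±4 (46 to 54).

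**The plan's own figures.** Nominal interval = visit day − 22, which gives 29 − 22 = 7, 36 − 22 = 14, 43 − 22 = 21 and 50 − 22 = 28. The labels are reproduced.

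**Range with every visit in window.** Literal reading: (earliest visit day − 24) to (latest visit day − 20). Boost-anchored reading: nominal interval ± the same window.

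| Visit | Literal reading, days after boost | Counted from boost |
|---|---|---|
| 6 | 26 − 24 = 2 to 32 − 20 = 12 | 4 to 10 |
| 7 | 33 − 24 = 9 to 39 − 20 = 19 | 11 to 17 |
| 8 | 39 − 24 = 15 to 47 − 20 = 27 | 17 to 25 |
| 9 | 46 − 24 = 22 to 54 − 20 = 34 | 24 to 32 |

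**How many date pairs are affected.** Visit 6 has 5 boost days × 7 visit days = 35 pairs. The pairs at 4 to 10 days number 5 + 6 + 7 + 6 + 5 = 29 (boost on Day 20 through Day 24), so 6 fall outside. Visit 9 has 5 × 9 = 45 pairs. Those under 28 days number 2 + 3 + 4 + 5 + 6 = 20. Those under 27 days number 1 + 2 + 3 + 4 + 5 = 15. These are counts of permitted dates, not probabilities.

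**Diary days lost.** Footnote n counts the boost day, so day 28 of the diary is boost + 27. Let Visit 9 be on Day 46, with that day covered by the visit itself.
- Boost Day 22: last diary day 22 + 27 = 49; Days 47 to 49 are lost, 3 days (3/28 = 11%).
- Boost Day 24: last diary day 24 + 27 = 51; Days 47 to 51 are lost, 5 days (5/28 = 18%).
- Boost Day 20: last diary day 20 + 27 = 47; 1 day is lost.
- Counted from boost: the earliest Visit 9 is boost + 24, so boost + 25 to + 27 are lost, 3 days.

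**Solicited reactions.** The 14 days end at boost + 13. Visit 8 is at least 15 days after an in-window boost, so this period is not cut short.

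**Delayed boost (Protocol 6.7).** If the boost is on Day 29 and Table 2 is not moved, the Visit 6 window runs from 26 − 29 = 3 days before the boost to 32 − 29 = 3 days after it. The last diary day would be 29 + 27 = 56, after the whole Visit 9 window. So 2 to 12 days is not an outer limit.

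**The case against.** The case against is substantial, and much of it stands.

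- **Anchor.** The column headings name the visits by days after boost, so a site may count from the boost. Visit 6 is then at 4 to 10 days, and most literal date pairs fall there anyway. This stands. It leaves the early diary closure in place (24 to 32 days) and shows that the anchor needs to be stated.
- **Primary endpoint.** A reader might infer that vaccine-related AEs in the gap are lost. The documents do not support that. Section 10.2.2 keeps collecting related AEs and SAEs, Table 2 marks AE recording at Visits 10 to 12, and SAP 7.1.2 already times AEs from the corresponding immunization date. The diary text itself requires 28 days, so this is an internal inconsistency and not a rule that shortens the endpoint. What remains is capture by recall at Month 3 (Day 85 ±7), possibly after the analysis triggered by Visit 9 (Protocol 13.2, SAP 7.10). Unrelated unsolicited AEs are less well protected, because beyond 28 days Section 10.2.2 asks only for related events and those leading to withdrawal.
- **Antibody error.** A reader might infer a several-fold error in early samples from the foreign RBD IgG ranges. Protocol 4.2.4 does not assign the pre-boost range to dose groups and gives no course between days 0 and 7 after the second dose, so no such figure can be derived.
- **Laboratory timing.** A reader might apply the foreign lymphocyte recovery at 6 to 8 days to Visit 6. That recovery is reported after the first dose only, and the post-prime laboratory visits are counted from the prime itself.
- **Day 28 results.** A reader might think mixed times are also pooled at Visit 9. No blood is drawn there, and no antibody or laboratory endpoint is set at that time.
- **Between-arm comparison.** Randomization and observer-blinding should keep visit timing similar across arms, and SAP 7.1 plans no formal testing. This stands for between-arm contrasts. It does not help the description of a 7-day response.

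**Conclusion.** The point holds as an inconsistency between the visit windows and the endpoints. On the literal reading, an in-window Visit 6 lies 2 to 12 days and Visit 9 lies 22 to 34 days after the boost; on the boost-anchored reading, 4 to 10 and 24 to 32 days. Either reading lets the last diary close before 28 days. With the boost day counted and Visit 9 on Day 46, the loss is 3 to 5 diary days for boosts on Days 22 to 24 (1 or 2 for earlier boosts). SAP 7.1.3 then reports Visit 6 antibody and safety laboratory results as Day 7 after boost regardless of the actual interval.

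These are permitted extremes. The documents give no distribution of actual visit dates, so the typical effect on the GMT, the laboratory proportions or the AE counts cannot be computed. The point is a worthwhile, inexpensive improvement and does not show that the primary endpoint fails.

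**What to change.** 1. **Protocol Table 2 (both schedules):** state that Visits 6 to 9 are counted from the actual boost date, including after a boost delayed under Section 6.7. With the present widths, the Visit 6 spread narrows from 10 days (2 to 12) to 6 days (4 to 10).
2. **Diary:** re-anchoring alone still allows closure at 24 days. Hold Visit 9 no earlier than completion of the 28 diary days, or have the subject keep the diary until they are complete.
3. **Protocol 10.2.2:** delete the trial-day translation of the post-boost period or reconcile it with Table 2 and footnote n.
4. **SAP 7.1.3:** report actual days since boost for Visit 6 and Visit 8 samples, and repeat the 7-day GMT with in-window samples only as a sensitivity analysis.

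The cost is schedule and SAP wording, a Visit 9 that falls a few days later for some subjects, and one extra table. When the boost itself is given does not change.
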